10.3 Safety Analysis

Not applicable.

11. QUALITY CONTROL

A quality assurance audit/inspection of this study may be conducted by the sponsor or sponsor's designees or by Institutional Review Board (IRBs) / Independent Ethics Committee (IECs) or by regulatory authorities.

Before analyses start, 200 randomly selected medical chart will be fully reviewed by well-trained experts to validate the accuracy and sensibility of code used to identify patients with cardiovascular disease or at high cardiovascular risk. This QC procedure for database study would be performed by [REDACTED].

In the procedure of data extraction, investigators will verify if the extracted data conform to predefined inclusion and exclusion criteria, 1000 records will be sampled randomly from extracted database;

Procedure of cleaning will be conducted according to the predefined reference range, unit, diagnosis code, and other standard;

The quality assurance auditor will have access to all results of the study, the investigator's study-related files and correspondence, and the informed consent documentation of this study.

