### **9.7.1 Main analysis**

Before analyses start, 200 randomly selected medical chart will be fully reviewed by well-trained experts to validate the accuracy and sensibility of code used to identify patients with cardiovascular disease or at high cardiovascular risk, chronic kidney disease and type 2 diabetes. This QC procedure for database study would be performed by [REDACTED].

The analyses will mainly describe the patient demographic characteristics, comorbidities, treatment pattern and economic burden based on 40 hospitals EMRs of Tianjin regional database. Descriptive data will be provided. The statistical methods and analyses will be described in detail in a Statistical and Epidemiological Analysis Plan (SEAP) prior to the commencement of any analyses.

Characteristics presented as continuous data will be summarized through means, standard deviations, medians, minimum and maximum values, whereas, categorical data will be summarized as counts and proportions.

All tests will be two-sided unless otherwise specified

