9.3.1 Exposure? (e.g. WHO Drug Dictionary, Anatomical Therapeutic Chemical (ATC) Classification System)				

Section 9: Data sources	Yes	No	N/A	Section Number
9.3.2 Outcomes? (e.g. International Classification of Diseases (ICD), Medical Dictionary for Regulatory Activities (MedDRA))				
9.3.3 Covariates and other characteristics?				
9.4 Is a linkage method between data sources described? (e.g. based on a unique identifier or other)				9.4

Comments:

--

Section 10: Analysis plan	Yes	No	N/A	Section Number
10.1 Are the statistical methods and the reason for their choice described?				9.7.1
10.2 Is study size and/or statistical precision estimated?				9.5
10.3 Are descriptive analyses included?				9.7.1
10.4 Are stratified analyses included?				
10.5 Does the plan describe methods for analytic control of confounding?				
10.6 Does the plan describe methods for analytic control of outcome misclassification?				
10.7 Does the plan describe methods for handling missing data?				
10.8 Are relevant sensitivity analyses described?				9.7.1

Comments:

--

Section 11: Data management and quality control	Yes	No	N/A	Section Number

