6.3 STUDY POPULATION

Diabetic/non-diabetic patients with/without established cardiovascular disease, chronic kidney disease, or at high cardiovascular risk.

Inclusion Criteria:

- 1) Patients in the Tianjin regional database from 01/01/2015 to 31/12/2019.
- 2) Group A: patients with diagnosis of diabetes, and with diagnosis of cardiovascular disease, heart failure, chronic kidney disease or at high cardiovascular risk;
- 3) Group B: patients with diagnosis of diabetes, but not with diagnosis of cardiovascular disease, heart failure, chronic kidney disease or at high cardiovascular risk;
- 4) Group C: patients with diagnosis of cardiovascular disease, heart failure, chronic kidney disease or at high cardiovascular risk, but not with diagnosis of diabetes;
- 5) Group D: patients without diagnosis of cardiovascular disease, heart failure, chronic kidney disease or at high cardiovascular risk, and without diagnosis of diabetes. We will randomly select a group of non-diabetic patients without any of the above diseases by matching on age and gender.

Definition of diabetes, cardiovascular disease, chronic kidney disease and high cardiovascular risk

- Diabetes: patients with at least 1 discharged diagnosis or 2 outpatient diagnosis of diabetes (ICD-10 E10-E14)
- Cardiovascular disease: patients with at least 1 discharged diagnosis or 2 outpatient diagnosis of ischemic heart diseases (ICD-10 I20~I25); or patients with at least 1 discharged diagnosis or 2 outpatient diagnosis of cerebrovascular diseases (ICD-10 I60~I69); or patients with at least 1 discharged diagnosis or 2 outpatient diagnosis of ischemic peripheral artery disease (ICD-10 E10.501, E11.603, E14.501, E14.606, E14.503, I73.9, I99.03, I99.04);
- Heart failure: patients with at least 1 discharged diagnosis or 2 outpatient diagnosis of heart failure (ICD-10 I50);
- Chronic kidney disease: inpatients with at least once 1 discharged diagnosis CKD (ICD-10 N18), or inpatients with the last estimated glomerular filtration rate (eGFR, calculated by CKD-EPI equation) <60 mL/min/1.73 m² or prescription of dialysis, but not with the diagnosis of acute kidney injury (ICD-10 N17); or outpatients with at least 2 diagnosis of CKD or with two consecutive eGFR (calculated by CKD-EPI equation) <60 mL/min/1.73 m² by 90 days or more.

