7.2.1 Primary outcomes

- 1) The proportion of diabetic/non-diabetic patients with established cardiovascular disease, chronic kidney disease, or at high cardiovascular risk.
- 2) The proportion of diabetic patients with established cardiovascular disease, chronic kidney disease, or at high cardiovascular risk among all patients with diabetes;
- 3) The proportion of non-diabetic patients with established cardiovascular disease, chronic kidney disease, or at high cardiovascular risk among patients without diabetes;

Table 1. The proportion of patients with disease or risk among diabetic or non-diabetic patients

| | 2015 | | 2016 | | ... | | 2019 | | Overall | |
|--|-----------------|----------------|-----------------|----------------|-----------------|----------------|-----------------|----------------|-----------------|----------------|
| | Outpatie nts | Inpatient s | Outpatie nts | Inpatie nts | Outpatie nts | Inpatient s | Outpatie nts | Inpatient s | Outpatie nts | Inpatient s |
| | n (%) | n (%) |
| Patients diagnosed with diabetes | | | | | | | | | | |
| Group A (n, %) | | | | | | | | | | |
| with cardiovascular disease | | | | | | | | | | |
| with chronic kidney disease | | | | | | | | | | |
| at high cardiovascular risk | | | | | | | | | | |
| Patients diagnosed without diabetes | | | | | | | | | | |
| Group C (n, %) | | | | | | | | | | |
| with cardiovascular disease | | | | | | | | | | |
| with chronic kidney disease | | | | | | | | | | |
| at high cardiovascular risk | | | | | | | | | | |

Note: Group A: Diabetes with cardiovascular disease, chronic kidney disease or at high cardiovascular risk; Group B: Diabetes without cardiovascular disease, chronic kidney disease or at high cardiovascular risk; Group C: Non-diabetes with cardiovascular disease, chronic kidney disease or at high cardiovascular risk; Group D: Non-diabetes without cardiovascular disease, chronic kidney disease or at high cardiovascular risk;

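### The 200-chart validation does not match the rules that build the primary outcome: the SAP omits diabetes and CKD, and the protocol's longer list does not fit the study definitions either

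*SAP*

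**What the plan says.** Both documents plan one review of 200 charts before the analyses start. SAP 11 gives its aim: "200 randomly selected medical chart will be fully reviewed by well-trained experts to validate the accuracy and sensibility of code used to identify patients". Protocol 9.7.1 states the same aim, but the two documents name different targets.

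- SAP 11 limits it to "code used to identify patients with cardiovascular disease or at high cardiovascular risk. This QC procedure for database study would be performed by" a named party.
- Protocol 9.7.1 has it cover the codes used to "identify patients with cardiovascular disease or at high cardiovascular risk, chronic kidney disease and type 2 diabetes".

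The classification being validated is defined in Protocol 9.2.2 and SAP 6.3.

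- Diabetes covers all types: "Diabetes: patients with at least 1 discharged diagnosis or 2 outpatient diagnosis of diabetes (ICD-10 E10-E14").
- CKD is not only a code. Besides N18, it admits "inpatients with the last estimated glomerular filtration rate (eGFR, calculated by CKD-EPI equation) <60" mL/min/1.73 m², a dialysis prescription, and for outpatients two low eGFR values at least 90 days apart.
- Heart failure (I50) is listed separately from CVD, and it places patients in Group A or C.

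The second primary outcome in SAP 7.2.1 is "The proportion of diabetic patients with established cardiovascular disease, chronic kidney disease, or at high cardiovascular risk among all patients with diabetes". The third is its counterpart in patients without diabetes.

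In Protocol Annex 2, the item "10.6 Does the plan describe methods for analytic control of outcome misclassification" is answered No. So are item 6.3 (validity of outcome measurement) and item 7.3 (information bias). Protocol 9.9 accepts that hospitals may understand ICD codes differently.

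**The concern.** Every primary result is a proportion whose numerator and denominator both come from an algorithm applied to hospital records. Diabetes status decides whether a patient is counted under outcome 2 or outcome 3, so an error there moves the patient between denominators. CKD is one of three conditions that qualify a patient for the numerator. If the review follows the SAP, neither is checked.

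With data on this scale, sampling error is small and classification error is likely to be the main uncertainty. The chart review is the only planned check, in the text available, of recorded status against the chart. The separate sample of 1000 records in SAP 11 checks extracted data against the eligibility criteria. It does not test whether the diagnosis is true.

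**Working it through.** **1. The plan's own figure.** The number 200 comes with no target sensitivity, PPV, interval width or prevalence, so there is nothing to reproduce. The check is what the 200 charts would cover and how precisely.

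**2. Coverage, side by side.**

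| Element | Study rule (Protocol 9.2.2, SAP 6.3) | Protocol 9.7.1 target | SAP 11 target |
|---|---|---|---|
| Diabetes | E10-E14, all types | type 2 only | not named |
| CVD | ischaemic heart, cerebrovascular and peripheral artery codes | named | named |
| Heart failure | I50, own category | not named | not named |
| CKD | N18, low eGFR or dialysis | named, as a code | not named |
| High CV risk | hypertension or hyperlipidaemia codes | named | named |

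Under the SAP, two of the five rows are covered. Under the protocol, all three numerator conditions are named, but diabetes is checked for one type only and the non-code routes to CKD are not mentioned.

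**3. Precision (assumed case counts).** The interval is exact Clopper-Pearson: for x successes in n, the limits are the 2.5% point of Beta(x, n−x+1) and the 97.5% point of Beta(x+1, n−x). If a share s of the 200 charts are true cases, n = 200 × s.

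- s = 5%, n = 10, observed 8/10: 44.4% to 97.5%
- s = 10%, n = 20, observed 16/20: 56.3% to 94.3%
- s = 20%, n = 40, observed 32/40: 64.4% to 90.9%
- all charts informative, 160/200: 73.8% to 85.3%
- all charts informative, 180/200: 85.0% to 93.8%

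For a half-width of 5 points, n = 1.96² × p(1−p) / 0.05². This gives 139 informative charts at p = 0.90 and 246 at p = 0.80. Two hundred charts are therefore reasonable for one common measure and thin for a rare one. Spread over the 40 hospitals they average 200/40 = 5 each.

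**4. What misclassification can do (assumed values).** With a correct denominator, apparent proportion = true × Se + (1 − true) × (1 − Sp).

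- True 0.70, Se 0.80, Sp 0.95: 0.56 + 0.015 = 0.575, a fall of 12.5 points
- True 0.70, Se 0.90, Sp 0.95: 0.63 + 0.015 = 0.645, a fall of 5.5 points
- True 0.50, Se 0.90, Sp 0.90: 0.45 + 0.05 = 0.50, no change, because the errors cancel

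For comparison, the 95% sampling half-width for a proportion of 0.5 in the protocol's 100,000 diabetic patients with comprehensive data is 1.96 × √(0.25/100,000) = 0.0031, or 0.3 points. With the 10,000 that SAP section 8 gives instead, it is 1.96 × √(0.25/10,000) = 0.0098, or 1.0 point.

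**5. Would an equal split by group repair precision?** Only partly. At the same observed 80%, 50 charts in a group give 40/50 = 66.3% to 90.0%, close to the 64.4% to 90.9% from 40 cases. Groups A and C also pool several conditions, so 50 charts per group do not guarantee any number of CKD or heart-failure cases.

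**The case against.** Several stronger readings are tempting, and the documents do not support them.

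- A reader might infer a simple random sample. The text says only that charts are randomly selected. The protocol sends further quality-control detail to the DMRP, which is not available here and may define a frame or strata. What stands is that the protocol and SAP state neither.
- A reader might infer that 200 charts cannot validate the codes. That fails for common conditions, as 180/200 shows. If the charts come from the four study groups, Group D equals Group A in size, so the share with diabetes or a listed condition is (A+B+C)/(2A+B+C), which is at least one half. Some targets may be well represented.
- A reader might infer that a poor result would change nothing. The review precedes the analyses, so code lists could still be revised. The documents are silent on the consequence. Checklist item 10.6 reports that no analytic control of misclassification is described. It does not mention the chart review, so it cannot show that the result goes unused. Some analysis sections, including Protocol 9.7.2 and SAP 10.2, are not in the available text.

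It can also be said that the protocol's longer list governs: version 3.0 is dated 18 June 2021, and Annex 1 dates the SAP 13 May 2021. But neither document says which prevails on this point, and the protocol's list still does not fit E10-E14, the eGFR and dialysis routes, or heart failure. One may read heart failure as part of CVD, but both documents now define it separately.

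Finally, in a descriptive study a corrected estimate is a choice rather than a requirement. That is fair, and it is why one supporting table is enough.

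**Conclusion.** The mismatch between the validation targets and the study rules is plain in the current text of both documents and rests on no assumption. Under the SAP wording, diabetes status and CKD would go unvalidated. Under the protocol wording they would be validated only in part. The absence of a stated frame, strata or use for the result holds for the available protocol and SAP text, and the DMRP could supply some of it.

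The effect on the primary proportions cannot be sized from the documents. The illustrations above run from no shift to 12.5 points, and they depend on assumed sensitivity, specificity and true proportion. The intervals for rarer conditions depend on an assumed 10 to 40 cases. This is a gap in coverage and specification that should be closed before the charts are pulled. It does not show that the codes are poor or that 200 charts are too few for every target.

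**What to change.** 1. Put one target list in Protocol 9.7.1 and SAP 11: diabetes by E10-E14, CVD, heart failure, CKD by the full study rule including the eGFR and dialysis routes, and high CV risk. Assess every chart for all five.
2. Keep 200 charts, but draw them by algorithm-defined status from the full eligible pool before Group D is matched, spread over hospitals. State the frame and the allocation.
3. Report PPV and NPV with exact 95% intervals, weighted to the unmatched pool. Do not weight to the study group sizes: Group D is fixed at the size of Group A by the 1:1 match and does not represent all unaffected non-diabetic patients.
4. Add one sensitivity table with the primary proportions under the observed misclassification. For stratum g with pool size N_g, let b_g be the share of charts confirmed as diabetic and a_g the share confirmed as diabetic with the condition. The adjusted outcome 2 is Σ N_g a_g / Σ N_g b_g. Outcome 3 uses the same form for patients confirmed as non-diabetic. This handles movement between denominators as well as numerator errors.

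The cost is two aligned paragraphs, a stratified draw, sampling weights and one table, with no extra charts. The drawbacks are that overall accuracy then needs weighting, and that precision for less frequent conditions, possibly CKD or heart failure, still depends on how many cases the draw contains.
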